### **3. STUDY DESIGN**

**Overview.** We propose to conduct a randomized, controlled trial among 100 men and women aged 60 or older with hyperkyphosis to an exercise intervention that includes kyphosis-specific spinal muscle strengthening exercises compared to a non-kyphosis specific stretching exercise control. The study will be conducted in five waves, with 10 participants in the exercise intervention and 10 participants in the control group in each wave.

The experimental and control interventions will be provided in small groups meeting three sessions per week for 6 months. At baseline and 6 months after the intervention, we will measure kyphosis, physical function, spine muscle strength and density, and quality of life. We will assess the effect of the intervention on the co-primary outcomes of kyphosis, Modified PPT (PPT) and gait speed measured as change over 6 months. We will also assess the effect of the intervention on secondary outcomes of physical function and HRQOL, measured as change in Timed Up and Go, Timed Loaded Standing, Six-Minute Timed Walk, the Scoliosis Research Society SRS-30 (self image domain) and PROMIS Physical Function and Global Health. Furthermore, we will investigate whether changes in kyphosis, spinal muscle strength and/or density

mediate the effect of the intervention on change in physical function. After the 6-month intervention, both groups will continue their usual activity and we will assess the durability of the effects of the intervention at 1-year follow-up.

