## **9. STATISTICAL CONSIDERATIONS**

### **9.1 General Design Issues**

**Overview:** The primary analyses will be by treatment assignment, without regard to adherence to the intervention. Improvements in kyphosis, the Modified Physical Performance Test (PPT), and gait speed at 6 months will be co-primary endpoints. The Hochberg procedure will be used in testing the effect of treatment on these three endpoints. However, given fiscal and feasibility limitations on this

single-site study, tests of treatment effects on 5 additional physical function and HRQOL measures (Aim 2), as well as muscle strength and density (Aim 3), and all 9 comparisons at 1 year, will be regarded as secondary and analyzed without penalty for multiple comparisons, but with results clearly presented as hypothesis-generating.

In preliminary analysis, we will use t-, Wilcoxon, chi-square, and Fisher exact tests as appropriate to compare the treatment and control groups in terms of baseline age, gender, co-morbidities, vertebral fractures, physical activity and level of kyphosis. If between-group imbalances are found, sensitivity analyses will be conducted adjusting for the imbalanced covariates. However, the primary analysis will be unadjusted, to avoid inflation of type-I error and erosion of confidence due to model selection.

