### 9.2.1 Treatment Assignment Procedures

**Randomization:** After the run-in period, participants will be randomized to the intervention group or control group. Participants will be randomized in equal proportions to intervention or control using randomly permuted blocks of randomly selected size 4 stratified by age and gender. Treatment assignments will be generated prior to the study, then placed in order in sealed, opaque

envelopes with stratum-specific sequential ID numbers. Consenting participants fulfilling study eligibility criteria will be assigned the next available ID number for the appropriate gender and age stratum. The date and time each envelope is opened will be recorded in a log along with participant ID to ensure integrity of randomization

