## 9.5 Data Analyses

Analysis for Specific Aim 1: Analysis of covariance (ANCOVA) will be used to assess the effects of intervention on changes in measured kyphosis and PTT scores from baseline to the end of the 6 month intervention period, adjusting for the baseline levels of each outcome, as well as for wave of recruitment. Normality and equality of variance of the residuals will be checked.

Analysis for Specific Aim 2: We will also use analysis of covariance (ANCOVA) to assess the effect of intervention on changes from baseline to the end of the 6 month intervention period, in measured HRQoL, as measured by the spinal deformity specific SRS-30 and SF-36 health status instruments, and on secondary measures of physical function including gait speed, spinal extensor muscle strength, Timed Loaded Standing, and the Jug Test. The models will adjust for the baseline level of the outcome.

Analysis for Specific Aim 3: The approach for Aims 1 and 2 will be used to assess intervention effects on muscle strength and density. We will then use structural equation modeling to assess the pathways through which the intervention affects physical function. We hypothesize that changes in kyphosis, strength and density mediate the effect of the intervention on change in physical function. These analyses will also control for mediation by increases in physical activity and aerobic capacity, as well as potential confounders of the changes in kyphosis and strength including age, and baseline kyphosis severity, physical activity level and vertebral fractures. Minimum detectable effects: The sample of 100 will provide 80% power to detect between-group differences of 6.2 points in spinal muscle strength, measured as a percentage of body weight, or 18% of the baseline mean of 35%.

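### Section 9.5 adjusts Aim 1 for wave but gives a baseline-only model for Aim 2, which as written leaves co-primary gait speed without wave and spinal extensor strength with two candidate models

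*Combined protocol and SAP*

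**What the plan says.** Section 9.5 describes three analyses.

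- **Aim 1** (kyphosis and PPT): ANCOVA "adjusting for the baseline levels of each outcome, as well as for wave of recruitment".
- **Aim 2** (quality of life and secondary function): ANCOVA again, then "The models will adjust for the baseline level of the outcome". Wave is not mentioned. The outcomes listed here include gait speed and spinal extensor strength.
- **Aim 3** (strength and density): "The approach for Aims 1 and 2 will be used to assess intervention effects on muscle strength and density".

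Sections 1.1 and 9.1 make gait speed a co-primary endpoint, tested with kyphosis and PPT by the Hochberg procedure. Section 9.1 also states that "the primary analysis will be unadjusted, to avoid inflation of type-I error". The other Aim 2 and Aim 3 tests are to be "regarded as secondary and analyzed without penalty for multiple comparisons, but with results clearly presented as hypothesis-generating".

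On design, Section 3 says the study is "conducted in five waves, with 10 participants in the exercise intervention and 10 participants in the control group in each wave". Section 9.2.1 randomizes with "randomly permuted blocks of randomly selected size 4 stratified by age and gender"; wave is not a stratum. The documents give no reason for treating Aims 1 and 2 differently and no estimate of how much outcomes vary by wave.

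**The concern.** Wave is part of the design, and the plan itself treats it as worth adjusting for in Aim 1. Three things follow from leaving it out of the Aim 2 sentence.

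1. Gait speed, one of three co-primaries, falls under the Aim 2 text. Hochberg compares the largest p-value with 0.05, the next with 0.05/2 = 0.025 and the smallest with 0.05/3 = 0.0167. The gait-speed p-value can therefore affect the decision on the other two endpoints, and its model should be fixed and should match theirs.
2. Spinal extensor strength is listed under Aim 2 and analyzed again under Aim 3, where the cited approach could be either model. Two models for one outcome leave a choice that could be made after the data are seen.
3. If outcomes differ by wave, that variance stays in the residual and the intervals are wider than they need to be. Because wave is not a stratum, nothing described in Section 9.2.1 enforces the planned 10 + 10.

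**Working it through.** **1. Covariates by outcome, read literally**

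| Outcome | Status | Placed under (Section 9.5) | Baseline | Wave |
|---|---|---|---|---|
| Kyphosis, PPT | co-primary | Aim 1 | yes | yes |
| Gait speed | co-primary | Aim 2 | yes | not named |
| Spinal extensor strength | secondary | Aims 2 and 3 | yes | not named / unclear |
| Muscle density | secondary | Aim 3 | yes | unclear |
| Other Aim 2 outcomes | secondary | Aim 2 | yes | not named |

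**2. Does wave enter the plan's own precision figure?** Section 9.2 gives a detectable kyphosis difference of 2.2 degrees. Inputs from that section: SD 5 (taken as the SD before the baseline reduction), r = 0.8, 20% loss from 100 (40 per arm), 80% power, and alpha 0.05/3 two-sided for three co-primaries.

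MDE = (2.394 + 0.842) × 5 × √(1 − 0.8²) × √(2/40) = 3.236 × 3 × 0.2236 = 2.17

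The noncentral t version gives 2.21. The stated figure is reproduced from baseline adjustment alone, so wave plays no part in it.

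**3. Precision cost of omitting wave.** Let R² be the share of post-baseline residual variance due to wave. With balanced waves, and ignoring the cost of estimating the wave terms,

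SE without wave / SE with wave = 1/√(1 − R²)

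This gives 1.026, 1.054 and 1.118 at R² = 5%, 10% and 20%. The formula slightly overstates the gain, because four extra parameters take residual degrees of freedom from 80 − 3 = 77 to 73 and chance imbalance has a small price. Simulation allows for both (6,000 trials per setting, 80 analyzed, r = 0.8, loss unrelated to arm or wave):

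| R² (assumed) | 10 + 10 forced in each wave | Age-by-gender blocks of 4 only |
|---|---|---|
| 0 | 0.994 | 0.988 |
| 5% | 1.020 | 1.014 |
| 10% | 1.049 | 1.042 |
| 20% | 1.113 | 1.106 |

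The last column assumes four strata with shares 0.40, 0.30, 0.15 and 0.15, because Section 9.2.1 gives no age cut-points.

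**4. What this means for gait speed.** With SD 0.18 and r = 0.85 from Section 9.2, the baseline-only detectable difference is 3.236 × 0.18 × √(1 − 0.85²) × 0.2236 = 0.069 m/s. At R² = 10%, adding wave would bring it to 0.0686/1.05 to 0.0686/1.04, about 0.065 to 0.066 m/s.

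**5. Validity.** In every setting the mean estimate without wave was within about 0.003 SD of the true value of zero. At R² = 5–20% the type I error without wave was 0.033–0.048 at a nominal 0.05, so the test is valid and at most mildly conservative.

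**6. Wave imbalance.** With four assumed strata and blocks of 4 running across waves of 20, about 34% of waves split exactly 10/10 and about 19–20% are 12/8 or worse. The SD of the exercise-arm count is 1.2; simple 1:1 randomization of 20 would give √(20 × 0.25) = 2.2. The largest departure from 10 in any of the five waves averaged about 1.7 participants.

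**The case against.** The strongest reply is that this is shorthand. Aim 2 follows directly on the Aim 1 model, says ANCOVA will also be used, and does not say that baseline is the only covariate; Aim 3 speaks of a single approach. That reading is possible. But Aim 2 states its own covariate and leaves wave out, and an analyst following the text could go either way. The ambiguity itself stands.

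A second reply is that the stakes are low: the affected results are labeled hypothesis-generating and the tests are valid without wave. This is right for the true secondary outcomes. It does not cover gait speed.

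A reader might also infer more than the documents support:

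- *That the Aim 2 standard errors are too large.* This is conditional on a wave effect. If wave explains nothing, adding it makes them about 1% larger.
- *That wave imbalance distorts the Aim 2 estimates.* The expected imbalance is one or two participants per wave, it arises by chance, and the wider baseline-only interval already allows for the noise it adds.
- *That Aim 2 results would not be comparable with the co-primary ones.* In a linear model under randomization, the treatment coefficient targets the same mean difference with or without wave. Only precision changes.
- *That wave stands in for site.* Several class sites are listed, some pending, but nothing ties them to particular waves.

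**Conclusion.** The point holds as an inconsistency in model specification that is worth correcting, not as a threat to validity. Section 9.5 names wave for two co-primaries, omits it for the text covering the third, and leaves strength and density open.

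Omission brings no bias. It may cost precision: a standard error about 1–2% larger if wave explains 5% of residual variance, 4–5% at 10% and 11% at 20%. Including wave when it explains nothing costs about 1%. The R² values are assumptions, since the documents give no wave effect. The ratios also assume 80 analyzed, loss unrelated to arm or wave and, for the unforced allocation, four age-by-gender strata.

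The main reason to act is that the gait-speed and strength models should be settled in advance; the possible gain in precision is secondary.

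**What to change.** State one model in Section 9.5 for all 6-month comparisons in Aims 1 to 3, for example: *each outcome, explicitly including gait speed, spinal extensor strength and muscle density, will be analyzed by ANCOVA adjusted for the baseline value of that outcome and wave of recruitment.* Name gait speed with the other co-primaries and delete the baseline-only sentence.

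In Section 9.1, reword the statement that the primary analysis is unadjusted so that it means no adjustment beyond baseline value and wave. As it stands, it conflicts with the Aim 1 model.

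The cost is a few sentences, four degrees of freedom and about 1% in standard error if wave proves irrelevant. No new data are needed, because Aim 1 already requires wave to be recorded. The change should be made before outcomes are compared by arm.

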## **10. DATA COLLECTION AND QUALITY ASSURANCE**

### **10.1 Data Collection Forms**

We will use the PROMIS Global Health and Physical Function questionnaires to collect study data. The study instruments are below in the Supplement/Appendices Section at the end.

### **10.2 Data Management**

Overview of data management: Data will be entered/submitted by clinic staff and participants (where applicable) and tracked by project staff. Authorized project/clinic staff may also update data to correct errors. Data will be managed, queried, and secured by the UCSF Data Management Group (DMG), enabling simple real-time electronic data entry, timely identification and resolution of data discrepancies, and transforming data to SAS for viewing, reporting, and analyses.

Data collection and editing: data will be collected via web forms/surveys with REDCap® software and stored on mySQL/MS SQL databases. Data collected will be viewed via the password-protected study website. Every hour, pre-programmed error-checking programs scan incoming forms for completeness and data ranges. The results of the error-checking procedures are posted to the study web site, where study staff are notified to correct all errors.

Data monitoring reports: Data are monitored on an ongoing basis by the Data Management Group to produce a number of standard reports that are made available on the study website automatically, including recruitment reports comparing goal versus actual recruitment rates; adherence reports comparing the number of expected visits to actual visits; and participant retention reports indicating the number of participants active, completed, and lost.

Computer and data security: The UCSF Data Management Group network is privately maintained and hardware fire-walled, and none of the workstations or database servers can be directly addressed from outside the Local Area Network. All study data will be stored on SQL servers that are backed-up nightly to disk and mirrored to a “failover” site at a co-location facility in San Francisco. In addition, back-up copies of the entire enterprise are archived in Sacramento, CA by Recall, Inc. All servers are housed in a state-of the-art secure server room with controlled access. All servers are protected from viruses by Network Associates Netshield 4.x, Groupshield, and VirusScan Enterprise 7.x (McAfee, Santa Clara, CA.).

## 10.3 Quality Assurance

### 10.3.1 Training

[name] will provide standardized training to the licensed physical therapists and physical therapy students involved in teaching the exercise sessions. Verbal instructions for the exercise intervention, verbal reinforcement, repetitions and progression in the exercise intervention have been standardized in our previous pilot study, and these procedures will be reviewed periodically to maintain consistency with the protocol.

### 10.3.2 Monitoring

After each wave of the intervention, the study staff will meet to review protocol compliance, recruitment and retention, adverse events forms, data quality, and review consent forms for completeness.

Throughout the study, [name] will conduct unannounced drop in visits to the intervention and control group exercise and stretching classes to ensure ongoing consistent standardized implementation. To minimize other co-interventions, all participants will be asked to refrain from beginning any new recreational, exercise, or other treatments for kyphosis until the trial has ended.

Data quality will be assessed based on time to receipt of data and the proportions of missing, illogical and out of range variables.

Measure	Goal Value	Acceptable Value
• time to receipt of data	<4 working days	<10 working days
• time to resolution of queries	<2 working days	<7 working days
• missing variables	0	< 5%
• variables queried*	5%	<10%

\*excluding Adverse Event and Medication Forms that are expected to have pending queries for current or ongoing items

Every hour, pre-programmed error-checking programs scan incoming forms for completeness and data ranges. The results of the error-checking procedures are posted to the study web site, where study staff are notified to correct all errors.

## 11. PARTICIPANT RIGHTS AND CONFIDENTIALITY

## **11.1 Institutional Review Board (IRB) Review**

This protocol and the informed consent document (Appendix II) and any subsequent modifications will be reviewed and approved by the IRB or ethics committee responsible for oversight of the study. The consent form should be separate from the protocol document.

## **11.2 Informed Consent Forms**

At the beginning of the screening visit, a member of the research staff will review the consent form in detail with the patient and answer all questions before inviting the patient to sign the consent form. A photocopy of the signed consent form with the Experimental Subjects' Bill of Rights is given to the patient. Study personnel will review the content of the informed consent with each participant before they sign it. Participants will be asked to describe the benefits, risks and other options if they choose not to participate with the study personnel.

## **11.3 Participant Confidentiality**

In order to maintain participant confidentiality, the study will ensure that (1) the informed consent process is conducted appropriately and that informed consent is obtained prior to proceeding with any study procedures; (2) data are collected and analyzed per protocol requirements; (3) the privacy and confidentiality of study subjects is maintained. Participation in research can involve loss of privacy; however, the participant's names will not be included on questionnaires or other forms. It will be replaced by an identification number.

The following precautions will be taken to maintain participant confidentiality:

- °Data are coded; data key is destroyed at end of study.
- °Data are coded; data key is kept separately and securely.
- °Data are kept in locked file cabinet.
- °Electronic data are protected with a password.
- °Data are kept in locked office or suite.
- °Data are stored on a secure network.

## **11.4 Study Discontinuation**

The study may be discontinued at any time by the UCSF Institutional Review

Board (IRB), the National Institute of Aging, or the data safety monitoring board (DSMB) as part of their duties to ensure that research participants are protected.

## **12. COMMITTEES**

Data Safety Monitoring Board - DSMB

## **13. PUBLICATION OF RESEARCH FINDINGS**

All publications of study findings will be reviewed by the NIA publications committee prior to submission.

## **15. SUPPLEMENTS/APPENDICES**

### **I. PROCEDURES SCHEDULE**

Assessment	Phone Screen	Clinic Screen	Medical Screen	Run In	Test Visit 1 (Baseline)	Intervention/Control Visits (1-72)	Test Visit 2 (6 month)	Maintenance Period	Test Visit 3 (1year)
Informed Consent Form		X							
Group Orientation (explain study)		X		X					
Basic Demographics	X				X				
DXA					X				
Lateral Spine Radiograph					X		X		X
Medical History	X		X						
Screen (gait, kyphosis, safety assessment)		X							
Current Medications	X		X						
Contact primary care providers for OK			X						
Inclusion/Exclusion Criteria	X	X	X						
Enroll		X							
Randomize					X				
Intervention/Control Study Visit						X			
Kyphosis: Cobb angle of kyphosis					X		X		X
Kyphosis: Debrunner					X		X		X
Spinal muscle strength: Biodex computerized dynamometer					X		X		X

Assessment	Phone Screen	Clinic Screen	Medical Screen	Run In	Test Visit 1 (Baseline)	Intervention/Control Visits (1-72)	Test Visit 2 (6 month)	Maintenance Period	Test Visit 3 (1year)
Spinal muscle density: CT scans					X		X		
Functional Performance					X		X		X
Health-Related Quality of Life					X		X		X

### III. Other

#### 1. PROMIS Global Health Questionnaire

PROMIS v.1.0 - GLOBAL

#### Global Items

Please respond to each item by marking one box per row.

	Excellent	Very good	Good	Fair	Poor
Global01 In general, would you say your health is:.....	 5	 4	 3	 2	 1
Global02 In general, would you say your quality of life is: .....	 5	 4	 3	 2	 1
Global03 In general, how would you rate your physical health?.....	 5	 4	 3	 2	 1
Global04 In general, how would you rate your mental health, including your mood and your ability to think?.....	 5	 4	 3	 2	 1
Global05 In general, how would you rate your satisfaction with your social activities and relationships?.....	 5	 4	 3	 2	 1
Global06 In general, please rate how well you carry out your usual social activities and roles. (This includes activities at home, at work and in your community, and responsibilities as a parent, child, spouse, employee, friend, etc.).....	 5	 4	 3	 2	 1
Global07 To what extent are you able to carry out your everyday physical activities such as walking, climbing stairs, carrying groceries, or moving a chair?.....	 5	 4	 3	 2	 1
	Completely	Mostly	Moderately	A little	Not at all

© 2008 PROMIS Health Organization and PROMIS Cooperative Group

Page 1 of 2

## In the past 7 days...

	Never	Rarely	Sometimes	Often	Always						
Globo10 How often have you been bothered by emotional problems such as feeling anxious, depressed or irritable?.....	 1	 2	 3	 4	 5						
Globo15 How would you rate your fatigue on average? ....	 1	 2	 3	 4	 5						
Globo17 How would you rate your pain on average?.....	 0 No pain	 1	 2	 3	 4	 5	 6	 7	 8	 9	 10 Worst imaginable pain

## 2. PROMIS Physical Function Questionnaire

PROMIS Item Bank v. 1.0 – Physical Function – Short Form 20a

### Physical Function – Short Form 20a

Please respond to each item by marking one box per row.

		Without any difficulty	With a little difficulty	With some difficulty	With much difficulty	Unable to do
PFA11	Are you able to do chores such as vacuuming or yard work? .....	 5	 4	 3	 2	 1
PFA12	Are you able to push open a heavy door? .....	 5	 4	 3	 2	 1
PFA15	Are you able to dress yourself, including tying shoelaces and doing buttons? .....	 5	 4	 3	 2	 1
PFA24	Are you able to wash your back? .....	 5	 4	 3	 2	 1
PFA28	Are you able to dry your back with a towel? .....	 5	 4	 3	 2	 1
PFA31	Are you able to sit on the edge of a bed? .....	 5	 4	 3	 2	 1
PFA35	Are you able to wash and dry your body? .....	 5	 4	 3	 2	 1
PFA38	Are you able to get in and out of a car? .....	 5	 4	 3	 2	 1
PFB19	Are you able to squeeze a new tube of toothpaste? .....	 5	 4	 3	 2	 1
PFB22	Are you able to hold a plate full of food? .....	 5	 4	 3	 2	 1
PFB24	Are you able to run a short distance, such as to catch a bus? .....	 5	 4	 3	 2	 1

		Without any difficulty	With a little difficulty	With some difficulty	With much difficulty	Unable to do
PPC20	Are you able to shampoo your hair? .....	 5	 4	 3	 2	 1
PPC43	Are you able to get on and off the toilet? .....	 5	 4	 3	 2	 1
PPC46	Are you able to transfer from a bed to a chair and back? .....	 5	 4	 3	 2	 1
		Not at all	Very little	Somewhat	Quite a lot	Cannot do
PPA1	Does your health now limit you in doing vigorous activities, such as running, lifting heavy objects, participating in strenuous sports? .....	 5	 4	 3	 2	 1
PPA2	Does your health now limit you in bending, kneeling, or stooping? .....	 5	 4	 3	 2	 1
PPA5	Does your health now limit you in lifting or carrying groceries? .....	 5	 4	 3	 2	 1
PPC12	Does your health now limit you in doing two hours of physical labor? .....	 5	 4	 3	 2	 1
PPC36	Does your health now limit you in walking more than a mile? .....	 5	 4	 3	 2	 1
PPC37	Does your health now limit you in climbing one flight of stairs? .....	 5	 4	 3	 2	 1

